Title Page

TITLE: Differences in Elbow Stiffness Comparing Massage to Stretching in Tennis Players (DESMS)

Date: 7.7.25

MATERIALS AND METHODS

Description of Study Personnel and Research Participants

The primary investigator was a licensed physical therapist with 20 years of clinical experience and with 13 years of research and musculoskeletal imaging experience. The primary investigator trained all personnel associated with the study including administrative duties, participant screening, ultrasound SWE examination, and intervention procedures.

Thirty-two healthy recreational tennis players (12 male/20 female, mean age $=54.4\pm13.8$ yr, mean BMI = 25.69 ± 3.73) were randomized into the STM (n=16) or stretching group (n=16). The participants were recruited from local tennis clubs by flyers and word of mouth. Initial screenings of the study criteria were reviewed over the phone with interested candidates prior to participation. The inclusion criteria required; adults older than 18 years old and participants had to report playing tennis at least one time a week on average. The exclusion criteria included; prior upper extremity surgery within the last 6 months, any diagnosed upper extremity pathologies or injuries within the last 6 months, rehabilitative/medical treatment of the upper extremity in the past year, and unable to tolerate soft tissue massage or stretching treatments. The national tennis rating program identifies and describes the characteristics of tennis players on a scale of 1.5 (beginner) to 7.0 (touring professional)(Association, 2024). Seventy-two percent of participants had a national tennis rating of 3.0-3.5, 19% were rated 4.0-4.5, and 6% were rated 2.5, and 3% were rated 4.5. Before participation, all participants were fully informed of the purpose and experimental procedures and gave their written consent. This study was approved by the internal review board at the xxx (approval no: 20597767).

Procedures

All participants completed a general health history questionnaire, and demographic information including age, gender, arm dominance, frequency of tennis play, shoulder activity levels, national tennis rating program rating, weight, and height. While seated, participants dominant arm, defined as the serving arm, was placed in following resting position: shoulder at 70° of abduction, elbow at 90° of flexion, and forearm in pronation. Stiffness measures were obtained at rest on the dominant common extensor tendon (CET) using 2D SWE ultrasound imaging (GE Logiq S8, 9L, linear transducer). The side of the probe indicator along the transducer was placed directly over the lateral epicondyle while the distal end of the transducer was in line with the middle of the radiocarpal joint (Figure 1). Three images were taken and stiffness values were recorded for each image. The region of interest (ROI) on the CET was outlined on screen between the lateral epicondyle and head of the radius(Day and Merriman). The shear wave modulus was then automatically generated in kilopascals (kPa) (Figure 2). Following these measurements, the participants were given a 5-minute rest. For the purpose of establishing intra-rater reliability, a second set of resting measurements were taken.

After the two initial collections were taken, participants were randomized to either common wrist extensor stretching or soft tissue mobilization(STM). Participants undergoing stretching were placed in the following position: shoulder at 90° of flexion on plinth, elbow at 0° of extension, forearm in full pronation, and wrist flexion. Participants were asked to report the comfort level of wrist flexion as tolerable ',' strong but tolerable, 'uncomfortable', or 'intolerable'. The intensity was maintained at a 'strong but tolerable' level for consistency and efficacy (Ylinen, Kautiainen, Wiren, and Hakkinen, 2007). Participants underwent a self-stretch holding this position for 30 seconds and repeating 5 times with a 30 second rest between

repetitions yielding a total time of 5 minutes. Three images of tendon stiffness were measured again using SWE immediately after the intervention. Participants were then given a 15-minute rest period after the post-intervention measurements and then 3 images of stiffness of the CET were taken in resting position.

Participants randomized to the STM group received 5 minutes of petrissage (a deep kneading) with linked effleurage (more superficial strokes) on the dominant test side. Deep prep massage cream was used to minimize patient discomfort from skin friction. Participants were asked to report the intensity of the STM as 'completely tolerable', 'strong but tolerable', 'uncomfortable', or 'intolerable'. Similar to the self-stretching, the intensity of the STM was maintained at a 'strong but tolerable' level for consistency and efficacy"(Ylinen, Kautiainen, Wiren, and Hakkinen, 2007). After the STM, three tissue stiffness measures were taken using SWE. Participants were then given a 15-minute rest period after the post-intervention measurements and then 3 images of stiffness of the CET were taken in resting position.

Statistics

Statistical analysis included measures of central tendency and variability of the descriptive data for each of the groups using Statistical Package for the Social Sciences 25.0 (Chicago, Illinois). An *a priori* power analysis indicated that at an alpha level of 0.05, and a conventional large effect size of 1.4 for a power of 0.95, a minimum sample of 15 per group was required(Zhu et al., 2020). The Kolmogorov-Smirnov test revealed a normal distribution of data. Frequencies and unpaired t-test were used to compare group characteristics (STM vs self-stretching) prior to statistical analysis. Within examiner intraclass correlation coefficients (ICC (3, 1)) with 95% confidence intervals were calculated using a two way mixed model average

measure for absolute agreement. Standard error of the measure (SEM) and minimal detectable changes (MDC) were also calculated. A repeated measures ANOVA using one between variable group (STM or stretching) and one within variable group (initial, post-treatment, and 15 minutes post-treatment)) was used in the main analysis. Significance was set at $p \le 0.05$ with a Bonferroni correction.

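### Two resting stiffness sets precede randomisation, but the plan does not say which forms the single 'initial' level; using one alone would give up precision that averaging both could recover

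*Combined protocol and SAP*

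**What the plan says.** In the combined protocol and SAP, Procedures describes four resting measurement occasions on the dominant common extensor tendon. The first consists of three images. After a 5-minute rest there is another: "For the purpose of establishing intra-rater reliability, a second set of resting measurements were taken". The number of images in this second set is not stated. Allocation follows: "After the two initial collections were taken, participants were randomized". Three images are taken right after the intervention and three more after a 15-minute rest.

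The main analysis under Statistics is a repeated measures ANOVA with group as the between factor and "one within variable group (initial, post-treatment, and 15 minutes post-treatment" as the within factor. Four occasions therefore feed three levels. No sentence says which pre-randomisation set or sets supply the first level.

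On sample size, Statistics gives the inputs as "at an alpha level of 0.05, and a conventional large effect size of 1.4 for a power of 0.95" and arrives at 15 participants in each arm.

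**The concern.** The comparison of massage with stretching is in effect a between-arm difference in change from *initial*, so measurement error in the baseline enters every treatment estimate. The only role the text gives the second set is reliability, and the ANOVA has one pre-treatment level, so the natural reading is that one set serves as baseline and the other does not contribute to the treatment comparison.

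Both sets precede randomisation. Any drift between them is therefore equal in expectation in the two arms, and averaging them cannot bias the arm comparison. What is at stake is precision with 16 per arm, together with reproducibility: an analyst given the data and this text could not tell how to form the first level.

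**Working it through.** **The plan's own figure.** Inputs from Statistics: alpha 0.05 (sidedness not stated, two-sided assumed), standardised effect 1.4, power 0.95. A two-sample t-test with the exact noncentral t distribution gives 15 per group (power 0.959 at 15, 0.969 at 16). The normal approximation gives 2(1.960 + 1.645)²/1.4² = 13.3, so 14. The stated 15 reproduces. The calculation uses no baseline correlation, so it does not count on a second baseline set. The study randomised 16 per arm.

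**Change from baseline.** Let s² be the error variance of one set, equal and independent across sets, and t² the between-person variance in true response. Neither is in the document.

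- One baseline set: Var(change) = 2s² + t²
- Mean of two sets: Var(change) = 1.5s² + t²
- Proportional reduction: 0.5/(2 + k), where k = t²/s²
- Equivalent size per arm: 16(2 + k)/(1.5 + k)

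| k | Reduction in variance | 16 per arm acts like |
|---|---|---|
| 0 | 25% | 21.3 |
| 1 | 16.7% | 19.2 |
| 2 | 12.5% | 18.3 |
| 4 | 8.3% | 17.5 |
| 8 | 5.0% | 16.8 |
| 10 | 4.2% | 16.7 |

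**Power.** An effect with 80% power from one set has about 90%, 87% and 85% at k = 0, 1 and 2. For a true effect of 1.0 SD of single-set change, power is 0.781 with one set, 0.885 at k = 0 and 0.802 at k = 8. At the plan's 1.4 it goes from 0.969 to 0.993 and 0.976. In a simulated group-by-time F test (equal correlations, 16 per arm, 8,000 runs per setting, effect 0.8 SD of change), power rises from about 0.62 to 0.73.

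**Baseline as covariate.** Let ρ be the correlation between the two baseline sets and r that between one set and a post measure. Residual variance is 1 − r² with one set and 1 − 2r²/(1 + ρ) with the mean of two.

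- ρ = r = 0.6: 0.640 to 0.550, down 14%
- ρ = r = 0.8: 0.360 to 0.289, down 20%
- ρ = r = 0.9: 0.190 to 0.147, down 22%
- ρ = 0.9, r = 0.5: 0.750 to 0.737, down about 2%

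The first three lines set the baseline-post correlation equal to the between-set correlation, which means no individual variation in response. The last relaxes that.

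**Serially correlated error.** Suppose error is purely first-order autoregressive, with correlation φ between successive occasions. For change to the first post measure, in units of s² and with t² = 0:

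- Set 1 alone: 2 − 2φ²
- Set 2 alone: 2 − 2φ
- Mean: 1 + (1 + φ)/2 − (φ + φ²)

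At φ = 0.8 these are 0.72, 0.40 and 0.46. The mean beats set 1 but loses to set 2. The mean and set 2 break even at φ = 0.5.

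If a share q of the error is independent between sets, mean minus set 2 is −0.5q + (1 − q)(−0.5 + 1.5φ − φ²). The last bracket peaks at 0.0625 (φ = 0.75), so in this model the mean is at least as good as set 2 once q ≥ 0.0625/0.5625 = 1/9.

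**The case against.** The text never says that the second set is left out of the main analysis. It speaks of two initial collections and then names the ANOVA level with the same word, so the level may already be their mean. This stands. A reader might infer that the second set was in fact discarded; the document does not establish that, and the loss is conditional on one set having been used. If the mean was used, the remedy is a sentence saying so.

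One set per time level is also a coherent design: it keeps measurement error comparable across the ANOVA levels, and averaging makes it unequal. That is a real cost, though a modest one. In the simulation under equal correlations, the uncorrected F test with the averaged baseline rejected between 0.050 and 0.053 of null data sets at a nominal 0.05.

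Independent error between images taken minutes apart is an assumption. Under strong, purely serial correlation, averaging is no better than set 2 alone and can be somewhat worse. This stands too, but needs nearly all the error to be serial, and it helps only if set 2 is the baseline, which the plan does not say.

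Finally, the text reports completed work, so redefining the baseline now is a post hoc change to the main analysis. That calls for disclosure and a sensitivity analysis.

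**Conclusion.** The *initial* level is undefined. As written, it appears to use one of two available pre-randomisation sets. If so, the treatment comparison is less precise than the held data allow under independent set error: 25% of change variance at most, 12.5% at t² = 2s², about 4% to 8% at t² = 4s² to 10s², and about 2% to 22% in the covariate cases worked above. The document gives no SD, ICC or baseline-post correlation, so the value within these ranges, or below them if individual response varies still more, is unknown.

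Two stronger inferences are not supported. Half of the baseline occasions is not half of the information: even the ceiling of 25% of variance is a 13.4% reduction in standard error (1 − √0.75). Nor does this make the trial underpowered against its own target, since the 15 per group was calculated without the second set and power at 1.4 with 16 per arm is 0.969 from a single set. The gain matters for effects smaller than 1.4. This is an inexpensive improvement and a needed clarification, not an invalid analysis.

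**What to change.** In Statistics, define *initial* for the treatment comparison as the mean of all pre-randomisation images from both sets, and give the number of images in the second set. If this was already done, say so. Keep the two sets separate for the ICC, SEM and MDC.

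Because the averaged level has smaller error variance than the two post levels, test the between-arm change at each post time with its own error term, or apply a Greenhouse-Geisser correction to the ANOVA. If the definition is new, label it as made after data collection and report the single-set result as a sensitivity analysis, naming the set used.

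The cost is a few sentences and a re-run on data already held, with no new measurement. The downsides are unequal error variance across time levels, a post hoc change that must be disclosed, and little or no gain over set 2 alone if error is strongly serially correlated.

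### Does the stretching schedule miss its stated 5 minutes, and does that spoil the comparison with 5 minutes of massage?

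*Combined protocol and SAP*

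**What the plan says.** The schedule is in the Procedures section of the combined protocol and SAP. The stretching is self-administered ("Participants underwent a self-stretch"). Its hold pattern is given as "holding this position for 30 seconds and repeating 5 times with a 30 second rest between", and that sentence closes, after a page break, with the words "repetitions yielding a total time of 5 minutes". The first post-treatment imaging follows: "Three images of tendon stiffness were measured again using SWE immediately after the intervention".

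The massage arm "received 5 minutes of petrissage (a deep kneading) with linked effleurage (more superficial strokes) on the dominant test side". No rests are described. Three stiffness measures follow the massage, with no statement of how soon.

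In both arms the 15-minute rest is counted from the post-treatment imaging, and the last three images follow it.

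The only feature the text expressly likens between the arms is intensity: "Similar to the self-stretching, the intensity of the STM was maintained at a 'strong but tolerable' level".

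The Statistics section compares the randomized groups in a repeated measures ANOVA with three occasions: initial, post-treatment and 15 minutes post-treatment.

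**The concern.** Both arms carry a 5-minute label and the same intensity target, so a reader may take the trial as a time-matched comparison of techniques. Three things seem to undercut that.

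- With rests only between five holds, the total is below 5 minutes.
- The stretch is held for only part of the session, whereas the massage is described without pauses. A group difference could then reflect amount of treatment as well as technique.
- If a final rest is needed to reach 5 minutes, the stretching arm might be imaged 30 s after tension ends and the massage arm at once, so that measurement timing would differ by arm.

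If all this held, a group or group-by-time effect would mix modality with exposure and with imaging delay.

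**Working it through.** **Inputs, all from Procedures.** Hold 30 s; rest 30 s; repeated 5 times; stated stretching total 5 min = 300 s; massage 5 min = 300 s with no rests described.

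**Session length.** Total = holds × 30 s + rests × 30 s.

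| Reading | Sum | Total | Against 300 s |
|---|---|---|---|
| 5 holds, a rest after each | 5×30 + 5×30 | 300 s (5.0 min) | 0 |
| 5 holds, rests only between | 5×30 + 4×30 | 270 s (4.5 min) | −30 s (−10%) |
| First hold plus 5 repeats, rests between | 6×30 + 5×30 | 330 s (5.5 min) | +30 s (+10%) |

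The first reading reproduces the stated figure exactly. The other two miss it by 30 s in opposite directions. The table shows which readings agree with the stated total. It does not show which schedule was delivered, and that is for the investigator to state.

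**Active time.** Five holds: 5 × 30 = 150 s, and 150/300 = 0.50 of the massage time. Six holds: 6 × 30 = 180 s, and 180/300 = 0.60. The 150 s is the same whether the five-hold session lasts 270 s or 300 s. Settling the 30 s question between those two therefore leaves the active-time gap unchanged, and the gap remains with six holds too.

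**Imaging delay.** Side by side, the stretching text has imaging immediately after the intervention, and the massage text says only that measures were taken after it. Neither gives a delay in seconds. If the stretching session ends with a rest, its first image comes at least 30 s after the last hold. The corresponding massage delay is not stated, so a between-arm difference of 30 s cannot be derived. The 15-minute rest has the same stated starting point in both arms.

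**Effect on the analysis.** The ANOVA uses the randomized group and three labelled occasions. The sample size (15 per group) comes from an effect size of 1.4, alpha 0.05 and power 0.95. Neither uses a hold count, rest count or session length, so all three readings lead to the same model, test and required sample size.

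**The case for a change.** The strongest opposing argument sets the 30 s aside and rests on active time. On no reading is active time equal: stretching has at most 0.60 of the massage time. The title frames the study as massage against stretching, both arms are labelled 5 minutes and intensity is held level, so readers will tend to infer equal exposure. The wording and the total also fail to agree when read literally, and someone repeating the study could not be sure how many holds and rests to use.

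Much of this stands as description. The literal 270 s is correct arithmetic, the active-time gap is real, and a group difference should be read as a difference between two regimens, not between techniques at equal dose.

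It does not follow that the comparison is unsound. No passage claims a match on active time. Seconds of static hold and seconds of kneading are not a common unit of dose, so half the seconds is not shown to be half the treatment. Hold-and-rest cycles can fairly be seen as part of a stretching regimen. The timing argument fails because the text does not say that massage was imaged at once.

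The possible remedies also gain little. Re-zeroing the images to the last active treatment cannot be applied to images already taken, and the document reports in the past tense on 32 randomized participants. Reporting actual session times presumes they were recorded, which the document does not say. Narrowing the conclusion addresses text that this document does not contain.

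**Conclusion.** No change to the plan follows. The session-length issue is an ambiguity of 30 s (10% of the stated total) about one hold or rest, and one natural reading reproduces the 5 minutes exactly. The active-time gap, 150 s or 180 s against 300 s, is a fair caveat on interpretation. It does not arise from the ambiguity and contradicts nothing the document claims. A between-arm difference in imaging delay cannot be established from the text.

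The conclusion rests on three assumptions: that every stretching participant followed the same schedule, that the massage ran for its stated 5 minutes, and that results are read as comparing the two regimens as delivered. On those terms the randomized comparison and the planned ANOVA stand under any of the three readings. The schedule and its total still have to be reconciled in the Procedures text. That is a clerical point for the investigator and has no bearing on the analysis.

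### The intra-rater ICC is labelled as a single-measure coefficient but described as an average-measure one, and the averaged unit is not stated

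*Combined protocol and SAP*

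**What the plan says.** The Statistics section describes the reliability analysis in one sentence that crosses a page break. It begins "Within examiner intraclass correlation coefficients (ICC (3, 1)) with 95% confidence intervals were calculated using a two way mixed model average" and continues "measure for absolute agreement. Standard error of the measure (SEM) and minimal detectable changes (MDC) were also calculated". No formula is given for SEM or MDC, and no ICC, SD, SEM or MDC value is reported.

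The Procedures section describes the data behind it. At the first resting measurement, "Three images were taken and stiffness values were recorded for each image". After a 5-minute rest, "For the purpose of establishing intra-rater reliability, a second set of resting measurements were taken". Both sets came before allocation: "After the two initial collections were taken, participants were randomized".

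Each follow-up has one set of three images. For stretching, "Three images of tendon stiffness were measured again using SWE immediately after the intervention", and after a further 15 minutes "then 3 images of stiffness of the CET were taken in resting position". For massage, "After the STM, three tissue stiffness measures were taken using SWE", again with three images 15 minutes later. The documents do not say that images were averaged, or which unit entered the ICC.

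**The concern.** In the ICC(model, unit) notation the second index gives the number of measurements behind the score whose reliability is being stated. A 1 means a single measurement; an average-measure coefficient carries k in that place. The sentence uses the 1 and then specifies an average measure. The two coefficients have different values and different confidence intervals, so the sentence cannot be right on both counts as written.

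The score that needs a reliability figure is the one taken after treatment and at 15 minutes, which is one three-image set. A coefficient for the mean of two sets, or of six images, describes a more precise score than the trial uses at follow-up. A reader judging from the ICC, or from an MDC built on it, whether a stiffness change exceeds measurement error needs to know which score is meant.

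**Working it through.** The documents give no reliability figure to reproduce, so the check sets out the readings the wording allows and sizes each under stated assumptions.

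**Inputs from the documents.** Three images per set and two resting sets (Procedures); 32 participants (Description of Study Personnel and Research Participants), all taken here to have both resting sets.

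**Assumptions.** Single-set ICC r = 0.50, 0.80 or 0.95; single-set variance 1, so true variance is r and set error variance is 1 − r; independent image errors; no shift between the two sets.

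**Single-image ICC.** Image variance is r + 3(1 − r) = 3 − 2r, so the single-image ICC is p = r/(3 − 2r) = 0.250, 0.571, 0.864.

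**Reported ICC under each reading**

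| Reading | Formula | r = 0.50 | r = 0.80 | r = 0.95 |
|---|---|---|---|---|
| Average over the two sets | 2r/(1 + r) | 0.667 | 0.889 | 0.974 |
| Average over all six images | 6p/(1 + 5p) | 0.667 | 0.889 | 0.974 |
| Average over three images in a set | 3p/(1 + 2p) | 0.500 | 0.800 | 0.950 |
| Single measure between set means | r | 0.500 | 0.800 | 0.950 |

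The first two readings overstate the reliability of one set. The last two do not.

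**Confidence interval at r = 0.80.** This uses the F-based absolute-agreement interval with n = 32, k = 2, MSR = 1 + r = 1.8 and MSE = MSC = 1 − r = 0.2.
- Single measure: (1.8 − 0.2)/(1.8 + 0.2) = 0.80.
- Common term: k·MSC + (kn − k − n)·MSE = 0.4 + 30 × 0.2 = 6.4.
- Lower limit, F = 2.033: 32(1.8 − 2.033 × 0.2)/(2.033 × 6.4 + 32 × 1.8) = 0.63.
- Upper limit, F = 2.041: 32(2.041 × 1.8 − 0.2)/(6.4 + 32 × 2.041 × 1.8) = 0.90.
- Average of two sets: applying 2x/(1 + x) to the estimate and both limits gives 0.89 (0.77 to 0.95).

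At r = 0.50 the same steps give 0.19 to 0.72 for the single measure and 0.32 to 0.84 for the average.

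**SEM.** The SEM of one set is √(1 − r). Suppose SEM was computed as SD·√(1 − ICC) with the two-set average ICC, for which 1 − ICC = (1 − r)/(1 + r). The ratio to the single-set SEM then depends on the SD chosen:

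| SD used | Ratio | r = 0.50 | r = 0.80 | r = 0.95 |
|---|---|---|---|---|
| One set, 1 | 1/√(1 + r) | 0.816 | 0.745 | 0.716 |
| Two-set mean, √((1 + r)/2) | √(1/2) | 0.707 | 0.707 | 0.707 |
| Individual images, √(3 − 2r) | √((3 − 2r)/(1 + r)) | 1.155 | 0.882 | 0.751 |

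The ratio lies on both sides of 1. If SEM was instead taken straight from the set differences, the ICC label does not affect it. MDC follows SEM in proportion.

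**The case against.** The strongest defence is that the word average refers to the data: three values were recorded per image set, so the coefficient may be an average over those three images. Under independent image errors that coefficient equals the single-set ICC, describes the follow-up score correctly, and leaves only the index 1 wrong. The second resting set, taken expressly for reliability, makes this reading less natural but does not exclude it. A single-measure ICC between two three-image means is equally harmless, and there it is the description that needs correcting. Both defences stand as possibilities. Neither is written down, and under either one the sentence still needs correction.

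It is also fair to say that leaving out a standard SEM or MDC formula in a short methods text is a reporting gap, not an error in itself.

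A reader might go further and infer that SEM and MDC are too small by a definite percentage. The documents do not support that. The SD and the formula are unstated, and the ratios above show that even the direction is open.

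A reader might also infer that the trial's main result is weakened. It is not. The sample size of 15 per group rests on an effect size of 1.4, alpha of 0.05 and power of 0.95, with no ICC in it. The repeated measures ANOVA does not use the coefficient, and no decision in the documents rests on the MDC.

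**Conclusion.** The conflict between label and description is certain from the sentence itself, and nothing elsewhere resolves it. Its effect on the numbers is conditional. If the average is over two sets or six images, the reported ICC exceeds the reliability of one set by 0.17, 0.09 or 0.02 at assumed single-set ICCs of 0.50, 0.80 or 0.95 (0.667 − 0.500, 0.889 − 0.800, 0.974 − 0.950), with a confidence interval moved upwards to match. If it is over the three images of a set, or if set means were compared by a single-measure ICC, nothing is overstated.

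These sizes rest on assumed ICCs, independent image errors and no shift between sets; none is a figure from the trial. SEM and MDC may not describe a single set, but no percentage can be claimed. The point is minor: it limits how the reliability figures can be read and leaves the treatment comparison as it was.

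**What to change.** Average the three images within each set. Report the single-measure, absolute-agreement, two-way mixed ICC between the two resting set means with its 95% CI, and name it in those words. If an average-measure ICC is also shown, label it as the reliability of a two-set mean.

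Derive SEM and MDC for one three-image set and state the formulas. For example, take SEM as the SD of the set differences divided by √2, report the mean shift between sets beside it, and take MDC95 = 1.96 × √2 × SEM for a change between two single sets.

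The cost is one re-run on values already recorded and a corrected sentence in the Statistics section. The reported ICC may come out lower, and SEM and MDC may change in either direction. If the single-measure ICC between set means is what was run, the ICC sentence needs only rewording.

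### Plain Bonferroni controls error in this plan and must not simply be dropped, but Holm, or a prespecified closed test gated on group-by-time, gives more power at the same familywise error

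*Combined protocol and SAP*

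**What the plan says.** The Statistics section describes the main analysis as "A repeated measures ANOVA using one between variable group (STM or stretching") and "one within variable group (initial, post-treatment, and 15 minutes post-treatment"). The next sentence sets the significance level at 0.05 "with a Bonferroni correction". That is the whole multiplicity rule. The section does not name group-by-time as the primary test, does not make follow-up comparisons conditional on it, and does not say which or how many comparisons the correction covers.

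The sample size in the same section is set "at an alpha level of 0.05" with "a conventional large effect size of 1.4 for a power of 0.95", from which "a minimum sample of 15 per group was required". The description of participants says that they "were randomized into the STM (n=16) or stretching group (n=16").

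**The concern.** A reader learns when the arms differ, and for how long, from the follow-up comparisons and not from the overall F test. With 16 per arm, the threshold for those comparisons matters. Bonferroni tests each one at 0.05/2 = 0.025 if there are two, or 0.05/3 = 0.0167 if there are three. Two better rules are available. Holm's step-down procedure rejects everything that Bonferroni rejects, and sometimes more, with the same familywise error for any family. With exactly three times, a closed test gated on group-by-time lets each between-arm change contrast be tested at the full 0.05. The plan uses neither, so it can miss a real difference at one post-treatment time with no gain in its error guarantee over Holm.

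**Working it through.** **Inputs from the documents.** Two arms of 16; three times, two of them post-treatment; alpha 0.05; effect size 1.4; power 0.95; Bonferroni with no stated family or gate.

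**Assumptions not in the documents.** Normal data with SD 1 at each time; correlation 0.6 between the initial and each later time, and 0.8 between the two later times; a moderate arm difference of 0.8 SD at both later times. A second case uses correlations of 0.7 and 0.8.

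**1. The plan's own figure.** The normal approximation gives n = 2 × ((1.960 + 1.645)/1.4)² = 13.3, so 14 per group. The exact two-sided t test has power 0.946 at 14 and 0.959 at 15, so the stated 15 per group is reproduced. This point does not dispute that figure.

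**2. Does Bonferroni control anything here?** Under no true effect (correlations 0.6/0.8, 100,000 simulated trials), the chance of at least one false positive among the two between-arm change contrasts is:

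| Rule | Familywise error |
|---|---|
| Each at 0.05, no gate (Bonferroni simply deleted) | 0.080 |
| Bonferroni over two, no gate | 0.041 |
| Each at 0.05, only after significant group-by-time | 0.046 |

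**3. Why a gate suffices for change contrasts.** Let δ1 be the arm difference in change from initial to post-treatment, and δ2 the same from initial to 15 minutes. The third pairwise contrast is δ2 − δ1. If any two of the three are zero, all are zero, so every intersection of these nulls is the group-by-time null itself. By the closure principle, once group-by-time is significant at 0.05, each contrast may be tested at 0.05. Check: with one contrast null and the other effect 1.0 SD, the null contrast is rejected in 0.050 of trials.

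**4. Where the gate does not suffice.** With within-person correlation of 0.3 to 0.7 and tests at 0.05 after a significant interaction, familywise error is 0.083 to 0.090 for between-arm tests at all three times when only one time differs. It is 0.15 to 0.17 for the six within-arm time pairs when only one arm changes. Bonferroni keeps both at or below 0.05, and Holm guarantees the same bound.

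**5. Power for one change contrast, 16 per arm.** The SD of a change score is √(2 × (1 − 0.6)) = 0.894. The noncentrality at 0.8 SD is (0.8/0.894) × √(16/2) = 2.53. With 30 df, ungated power is 0.572 at 0.025 and 0.506 at 0.0167. Holm and the gated rules were simulated (interaction tested with Greenhouse-Geisser df):

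| Rule | 0.8 SD, 0.6/0.8 | 0.8 SD, 0.7/0.8 | 1.4 SD, 0.6/0.8 |
|---|---|---|---|
| Gate + Bonferroni over three | 0.51 | 0.65 | 0.964 |
| Bonferroni over two, no gate | 0.57 | 0.71 | 0.976 |
| Holm over two, no gate | 0.63 | 0.76 | 0.986 |
| Gate + each at 0.05 (closed test) | 0.65 | 0.78 | 0.988 |

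From Bonferroni over two, Holm adds about 5 to 6 points at 0.8 SD and the closed test about 7 to 8. At 1.4 SD they add 1.0 and 1.2 points. The closed test gains 2.4 points over the three-way correction.

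**6. A ceiling at 1.4.** If 1.4 is read as a plain two-sample difference at one time, power with 16 per arm is 0.969 at 0.05, 0.939 at 0.025 and 0.915 at 0.0167. No improved rule could then recover more than 0.969 − 0.939 = 3.0 points over a two-way correction, or 0.969 − 0.915 = 5.4 over a three-way one.

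**The case against.** A reader might infer the stronger claim: that Bonferroni is redundant after the ANOVA, because the interaction test already controls the follow-up family, and so can be struck out. The documents do not support this. They contain no gate, and without one the error for two contrasts at 0.05 is about 0.08. They also do not define the family. If it includes within-arm time pairs or between-arm tests at each time, even a gate leaves the error well above 0.05. This objection defeats plain deletion. It also confines the closed test to between-arm change contrasts. It does not touch Holm, which needs no gate and is valid for any family.

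Three further points can be made for the plan. Bonferroni is valid, and it has matching simultaneous confidence intervals, which Holm and the closed test lack. That stands as a cost, although the section mentions no intervals for these contrasts. The gain is small at the effect size the trial planned for, and the larger figures rest on assumed values; that stands too. Finally, the text is in the past tense and already reports the outcome of the normality check, so data seem to have been in hand. Moving to a more liberal rule after seeing results is open to challenge. That limits how a change can be presented, not whether the rule is better.

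**Conclusion.** The point holds as a cheap improvement and not as an error in the plan. Bonferroni protects the familywise error as the plan stands, but Holm gives the same protection and never rejects less. A prespecified gate does slightly better for the two between-arm change contrasts. The benefit is about 5 to 8 points of power per contrast at an assumed 0.8 SD, and about 1 to 2 points at 1.4 SD. These sizes depend on the assumed correlations and on a family of two contrasts. That Holm rejects at least as much as Bonferroni, and that closure is valid with three times, do not depend on them.

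**What to change.** Name the family and replace plain Bonferroni with Holm. Suggested wording: 'The between-arm differences in change from initial to post-treatment and from initial to 15 minutes will be tested with Holm's procedure at a familywise level of 0.05.'

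Alternatively, prespecify a gate: 'Group-by-time will be tested at 0.05. Only if it is significant will the two between-arm differences in change each be tested at 0.05, as a closed test.' Under this option, any within-arm time comparisons, or between-arm tests at each of the three times, form a separate family with its own Holm correction. The between-arm comparison at the initial time need not be in the family: allocation followed the initial measurements, so its null is true by randomisation.

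The cost is one or two sentences and no new data. Ordinary 95% intervals would be reported and labelled as unadjusted. If the sponsor values simultaneous intervals more than the added power, keeping Bonferroni over a named family is defensible. If results have already been seen, show the Bonferroni result as planned and label the Holm or closed-test result post hoc.
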